4.1 Study Treatments

Treatment administration for nivolumab and ipilimumab (a ± 2 -day window will be allowed):

Table 4.1-1: Treatment Administration

Cohort/Arm	Dose	Infusion Time
1 and 2	3 mg/kg nivolumab every 2 weeks	60 minutes
A	1 mg/kg nivolumab + 3 mg/kg ipilimumab every 3 weeks x 4 doses and then 3 mg/kg nivolumab every 2 weeks	Part 2: nivolumab 60 minutes + 30 minutes break ipilimumab 90 minutes and then nivolumab 60 minutes
		Part 3: nivolumab 30 minutes + 30 minutes break ipilimumab 30 minutes and then nivolumab 30 minutes
B	3 mg/kg nivolumab every 2 weeks	30 minutes
D	1 mg/kg nivolumab + 3 mg/kg ipilimumab every 3 weeks x 4 doses and then 3 mg/kg nivolumab every 2 weeks	nivolumab 30 minutes + 30 minutes break ipilimumab 30 minutes and then nivolumab 30 minutes
E	3 mg/kg nivolumab every 2 weeks	30 minutes

Table 4.1-2: Product Description

Product Description and Dosage Form	Potency	Primary Packaging (Volume)/ Label Type	Secondary Packaging (Qty) /Label Type	Appearance	Storage Conditions (per label)
BMS-936558-01 Solution for Injection	100 mg (10mg/mL)	10 mL/ open label	10 vials per box/ open labels	Colorless to pale yellow, clear to opalescent solution; may contain particles	Store Refrigerated, 2-8° C (36-46 F) Protect from light and freezing.
Ipilimumab Solution for Injection	200 mg (5 mg/mL)	40 mL per vial/Open- label	4 vials per carton/Open-label	Clear, colorless to pale yellow liquid. May contain particles	2 to 8°C. Protect from light and freezing.

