4.3.4 Dose Delay Criteria

Study drug administration should be interrupted and increased monitoring of subjects should ensue if any of the following drug related adverse event(s) occurs:

- Any persistent grade ≥ 2 non laboratory non-skin drug related adverse event except for fatigue and weakness
- Any grade ≥ 2 endocrine drug-related adverse event
- Any grade ≥ 3 skin drug related adverse event

- Any Grade ≥ 3 drug-related laboratory abnormality (except lymphopenia, asymptomatic lipase or amylase increases, or any electrolyte abnormality without any clinical sequelae that is either spontaneously reversible or resolves with clinical management to grade 2 or less within 72 hours)
- ALT or AST $> 3X$ ULN (treatment may resume when the AE resolves to Grade 1)
- Patients with pre-existing neurologic or ophthalmologic anti-CTLA4 related adverse event who develop clinical symptoms leading to a 1 grade drug related shift (i.e. grade 1 to grade 2)
- Any AE, laboratory abnormality or inter-current illness which, in the judgment of the investigator, warrants skipping the dose of study medication

If dose delay is necessary, both nivolumab and ipilimumab must be delayed until treatment can resume. If a delay prevents subsequent infusion of ipilimumab, the dose of ipilimumab should be replaced as soon as possible. At least 19 days must elapse between the replacement dose of ipilimumab and the administration of the next dose of the combination.

The occurrence of clinically meaningful drug related AEs requires early recognition and prompt intervention. Management algorithms are available for suspected pulmonary, gastrointestinal, hepatic, renal, endocrine, neurological and skin toxicities. The recommendation is to follow the nivolumab IB adverse event algorithm. The algorithms can also be found on [Appendix 4](#).

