4.3.5 Study Drug Discontinuation Criteria due to Adverse Event(s)

Study drug administration must be discontinued if at least one of the following drug related adverse event(s) occurs:

- Any \geq Grade 2 eye pain or reduction of visual acuity that does not respond to topical therapy and does not improve to Grade 1 severity within 2 weeks of starting therapy OR requires systemic treatment;
- Any \geq Grade 3 non laboratory drug-related adverse event with the exception of fatigue, and endocrine drug related AEs which are stable with hormone replacement therapy
- Any \geq Grade 3 bronchospasm, hypersensitivity reaction, or infusion reaction;
- Any patient that experiences any grade allergic/infusion reaction while receiving study drug at a slower infusion rate and/or with premedication due to a prior allergic/infusion reaction
- Any drug-related Grade 4 laboratory abnormalities, (except lymphopenia, asymptomatic lipase or amylase increases, or any electrolyte abnormality without any clinical sequelae that is either spontaneously reversible or resolves with clinical management to grade 2 or less within 72 hours)

- Hepatotoxicity as evidenced by any of the following:
 - AST or ALT > 5 - 10x ULN for >2 weeks
 - AST or ALT > 10 ULN
 - Total bilirubin > 5 x ULN
 - Concurrent AST or ALT > 3 x ULN and total bilirubin > 2 ULN (potential Hy's Law case)
- Any adverse event, laboratory abnormality or intercurrent illness, which in the judgment of the Investigator, presents a substantial clinical risk to the subject
- All adverse events that meet discontinuation criteria, as well as any Grade 3 or 4 infusion reactions must be reported to BMS, within 24 hours using the rapid notification procedures described in [Section 6.1.1](#).

Subjects who experience AEs that require discontinuation while receiving both nivolumab and ipilimumab may be allowed to continue therapy with nivolumab only if deemed in their best interest by both the PI and the BMS medical monitor. This will be decided on a case by case basis and will require convincing evidence that the benefit outweighs the risk.

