Survival Status	X	Survival status should be continued every 3 months for the time remaining after the last office follow-up visit until 2 years from the first dose of BMS-936558 or until subject death, subject withdraws consent, subject is lost-to follow-up or the study is completed. This may be accomplished by visit or phone contact.

Table 5.1D: On Treatment Procedural Outline (CA209038) - Part 2, Part 3 and Part 4: Arms A and D								
[Procedure Window ± 2 days]								
Procedure	Wk1 Day 1	Wk4 Day 1	Wk7 Day 1	Wk10 Day 1	Wk 13 Day 1 and every 2 weeks thereafter	End of Therapy	Follow- Up Visits 1 and 2^a	Notes
Safety Assessments								
Targeted Physical Examination	X	X	X	X	X	X	X	To be performed only as clinically indicated
Vital Signs and Oxygen Saturation	X	X	X	X	X	X	X	Including BP, HR, temperature and oxygen saturation by pulse oximetry. Pulse oximetry at rest and after exertion within 72 hours prior to dosing
Physical Measurements (including performance status)	X	X	X	X	X	X	X	Weight and ECOG performance status
Adverse Events Assessment	X	X	X	X	X	X	X	Continuously throughout the study
Review of Concomitant Medications	X	X	X	X	X	X	X	
12 Lead ECG					X*			*To be performed pre-dose at Week 13, Week 23 and then every 16 weeks thereafter

Table 5.1D: On Treatment Procedural Outline (CA209038) - Part 2, Part 3 and Part 4: Arms A and D									
[Procedure Window ± 2 days]									
Procedure	Wk1 Day 1	Wk4 Day 1	Wk7 Day 1	Wk10 Day 1	Wk 13 Day 1 and every 2 weeks thereafter	End of Therapy	Follow- Up Visits 1 and 2 ^a	Notes	
Laboratory Tests									
Serum Chemistry	X	X	X	X	X		X	X	Within 72 hours prior to re-dosing to include: Aspartate aminotransferase (AST), Alanine aminotransferase (ALT), total bilirubin, alkaline phosphatase, lactate dehydrogenase, creatinine, blood urea nitrogen (BUN) or serum urea level, amylase, lipase, glucose, sodium, potassium, chloride, CO ₂ calcium, magnesium, TSH (if TSH is abnormal then obtain free T3 and free T4), ACTH collected in the morning as clinically indicated.
Hematology	X	X	X	X	X		X	X	Within 72 hours prior to re-dosing to include CBC with differential NOTE: Additionally required for the PBMC sample collection at the following timepoints: Week 1 Day 4; Week 2 Day 1; Week 3 Day 1; and Week 5 Day 1
Pregnancy Test (WOCBP only)	X	X	X	X	X	X	X	X	Serum or urine within 24 hours prior to administration of study drug

Table 5.1D: On Treatment Procedural Outline (CA209038) - Part 2, Part 3 and Part 4: Arms A and D								

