7.4.1 Study Therapy

The following calculations will not be performed for the subject enrolled in Arm C prior to the closure of that arm in Amendment 06.

Summary:

Descriptive statistics will be provided by part and cohort/arm for the following.

- Nivolumab
 - Number of doses of nivolumab
 - Duration of therapy (weeks) of nivolumab = last dose date - start dose date + 14)/7, only calculated if:
 - ◆ Nivolumab is taken as a monotherapy (Part 1, Arm B, and Arm E)
 - ◆ Nivolumab and ipilimumab combination therapy if the last dose is nivolumab monotherapy (ie, after the 4th dose in Arms A and D).
 - Duration of therapy (weeks) of nivolumab = (last dose date - start dose date + 21)/7, only calculated if:
 - ◆ Nivolumab and ipilimumab combination therapy if the last dose is a combination therapy (ie, the first 4 doses in Arms A and D).
 - Cumulative dose (mg/kg) of nivolumab = the sum of all actual nivolumab doses that a subject received
 - ◆ The actual doses received is documented in mg, so prior to taking the sum, the actual dose needs to be divided by the subject’s weight at baseline, unless their weight at the most recent visit differs by 10% or more compared to baseline
 - Relative dose intensity (%) = cumulative dose (mg/kg) / [3 mg/kg*(last dose date - start dose date + 14)/14]*100, only calculated if nivolumab is taken as a monotherapy (Part 1, Arm B, and Arm E).
 - ◆ Categories: < 50%; 50 - < 70%; 70 - < 90%; 90 - < 110%; ≥ 110%
 - Relative dose intensity (%) = cumulative dose (mg/kg) / [1 mg/kg*(last dose date - start dose date + 21)/21]*100, only calculated if nivolumab is taken as a combination therapy (Arms A and D) and subject’s last dose is in the combo phase.
 - ◆ Categories: < 50%; 50 - < 70%; 70 - < 90%; 90 - < 110%; ≥ 110%
 - Relative dose intensity (%) = cumulative dose (mg/kg) / [1 mg/kg*4 cycles + 3 mg/kg*(last dose date - 84 + 14)/14]*100, only calculated if nivolumab is taken as a combination therapy (Arms A and D) and subject’s last dose is in the mono phase.
 - ◆ Categories: < 50%; 50 - < 70%; 70 - < 90%; 90 - < 110%; ≥ 110%
- Ipilimumab
 - Number of doses of ipilimumab

- Duration of therapy (weeks) of ipilimumab = (last dose date - start dose date + 21)/7.
- Cumulative dose (mg/kg) of ipilimumab = the sum of all actual ipilimumab doses that a subject received

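### The SAP's mono-phase nivolumab dose-intensity formula gives meaningless values for Arm A and D subjects who switch early to nivolumab alone and have their last dose before day 70

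*SAP*

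**What the plan says.** SAP 7.4.1 uses different nivolumab RDI formulas according to where treatment ended. For a subject in Arm A or D who ends in the combination phase it is "cumulative dose (mg/kg) / [1 mg/kg*(last dose date - start dose date + 21)/21]*100". For one whose "last dose is in the mono phase", it is "cumulative dose (mg/kg) / [1 mg/kg*4 cycles + 3 mg/kg*(last dose date - 84 + 14)/14]*100". The second formula has no start date, and no term for the subject's own number of combination doses or switch date. Results are sorted into five classes, from below 50% to 110% and above.

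The RDI bullets do not define the mono phase. The nearest gloss is in the duration bullet: "if the last dose is nivolumab monotherapy (ie, after the 4th dose in Arms A and D".

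The constants come from the planned regimen. Protocol Table 4.1-1 has "1 mg/kg nivolumab + 3 mg/kg ipilimumab every 3 weeks x 4 doses and then 3 mg/kg nivolumab every 2 weeks", and Table 5.1D places the first nivolumab-alone dose in the column headed "Wk 13 Day 1 and every 2 weeks thereafter".

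The protocol allows departures from that plan. Under 4.3.5, subjects with an adverse event requiring discontinuation while on both drugs "may be allowed to continue therapy with nivolumab only if deemed in their best interest by both the PI and the BMS medical monitor". That section gives neither dose nor interval; SAP 6.1.2 has nivolumab every 2 weeks in Arms A and D once ipilimumab has stopped. On delays, Protocol 4.3.4 says "If dose delay is necessary, both nivolumab and ipilimumab must be delayed until treatment can resume", and 4.3.6 normally requires re-treatment within 6 weeks of the previous dose.

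**The concern.** The denominator of an RDI should be a planned dose, so it must be positive and must grow sensibly with time on treatment. Here it is built on the premise that every subject who reaches nivolumab alone had four combination doses in 84 days. A subject who switches after one, two or three combination doses can have a last dose well before day 84. The formula then subtracts 3 mg/kg per 14 days for time that has not yet elapsed.

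At stake is the nivolumab RDI table and by-subject listing for the combination arms. A negative RDI has no meaning and would drop into the below-50% class. A value of several hundred percent goes into the top class. Both would come from subjects who left the combination because of toxicity.

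**Working it through.** **Inputs.** The formulas are from SAP 7.4.1; the regimen is from Protocol Tables 4.1-1 and 5.1D. Let L = days from first to last dose and M = days from first dose to first nivolumab-alone dose. The last dose date in the formula is read as L, which restores the missing start date.

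**Step 1: the SAP denominator.** D(L) = 4 + 3 × (L - 84 + 14)/14 = 4 + 3 × (L - 70)/14. It is zero at L = 70 - 56/3 = 51.3, so it is negative up to day 51.

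**Step 2: on-schedule check.** The 84 days are 4 × 21, which is Week 13 Day 1. Four combination doses plus one nivolumab-alone dose: L = 84, 7 mg/kg given, D = 7, RDI 100%. One more dose: L = 98, 10/10 = 100%. The constants are right for the planned course.

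**Step 3: what the assigned regimen schedules.** Through day L + 14, the prorated planned dose is S(L) = min(L + 14, 84)/21 + 3 × max(L + 14 - 84, 0)/14. For L of 70 or more, S(L) = 4 + 3 × (L - 70)/14 = D(L). Below 70, S(L) = (L + 14)/21, and D(L) is smaller: at L = 63, D = 2.5 against S = 77/21 = 3.67.

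**Step 4: early switchers.** Assumptions: combination doses every 21 days, first nivolumab-alone dose 21 days after the last combination dose, then 3 mg/kg every 14 days. With c combination and k nivolumab-alone doses, L = 21c + 14(k - 1) and the cumulative dose is c + 3k. The own-phase denominator is M/21 + 3 × (L - M + 14)/14.

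| c + k | L | Given (mg/kg) | D(L) | SAP RDI | S(L) | RDI against S | Own-phase RDI |
|---|---|---|---|---|---|---|---|
| 2 + 1 | 42 | 5 | -2 | -250% | 2.67 | 188% | 100% |
| 2 + 2 | 56 | 8 | 1 | 800% | 3.33 | 240% | 100% |
| 1 + 4 | 63 | 13 | 2.5 | 520% | 3.67 | 355% | 100% |
| 3 + 1 | 63 | 6 | 2.5 | 240% | 3.67 | 164% | 100% |
| 2 + 3 | 70 | 11 | 4 | 275% | 4 | 275% | 100% |
| 2 + 5 | 98 | 17 | 10 | 170% | 10 | 170% | 100% |

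The first four rows are wrong on either benchmark. The last two are exact ratios to the assigned schedule.

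**Step 5: sensitivity.**
- *Gap.* For 2 + 1 doses, gaps of 14, 28 and 42 days give -143%, -1000% and 200%. After three combination doses and a gap of at least 14 days the value is never negative; with a 42-day gap L is 84 and the formula works (6/7 = 86%).
- *Dose.* D(L) does not depend on the dose given, so the sign does not change. At 1 mg/kg every 14 days, used only as a test value, 2 + 1, 2 + 2 and 1 + 4 give -150%, 400% and 200%.
- *Meaning of mono phase.* If it means after the fourth dose, 2 + 1 and 2 + 2 go to the combination formula: 5/(63/21) = 167% and 8/(77/21) = 218%. The negatives disappear. The fifth dose of 1 + 4 still uses the mono formula and still gives 520%.

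**The case against.** The strongest reply is that the denominator is a legitimate benchmark. From day 70 it equals what the assigned regimen schedules. If an early switcher receives 3 mg/kg every 2 weeks while the arm schedules 1 mg/kg every 3 weeks, nivolumab exposure really is above plan, and 275% or 170% says so. This stands.

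A reader might also infer that delays in the combination phase are mis-scored. With four combination doses, one 21-day delay and four nivolumab-alone doses, L = 147 and the SAP gives 16/20.5 = 78%, against 16/(105/21 + 12) = 94% on the subject's own phases. But 78% is the exact ratio to the assigned schedule. Charging the delay at the mono rate is a choice of benchmark, and the documents do not make it an error.

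The second reply is that the SAP's only gloss places the mono phase after the fourth dose, which removes every negative. That stands too, but it does not rescue the formula, because 520% for 1 + 4 remains against 355% on the assigned schedule.

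Third, RDI is descriptive. It is not among the safety endpoints in SAP 4.2.1, and dose counts, cumulative dose, duration, delays and discontinuations are reported separately. That stands and sets the priority.

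**Conclusion.** The point holds for a defined subset: Arm A or D subjects who switch early to nivolumab alone and whose last dose comes before day 70 after the first. For them the mono-phase formula, with the start date restored, gives a negative RDI (last dose by day 51) or an inflated one (day 52 to 69). The quoted sizes assume 3 mg/kg every 14 days after the switch and a 21-day gap. The negatives also assume that the mono phase means that the last dose was nivolumab alone.

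A reader might infer that all early switchers get absurd values, that all of roughly 50 subjects in Arms A and D (20 + 20 + 10) are affected, or that the tolerability objective is compromised. The documents support none of these. From day 70 the value is above 100% by a shrinking amount and is a true ratio to the assigned schedule. On-schedule subjects get exactly 100%. Protocol 4.3.5 allows the switch only case by case, so the number of switchers is unknown. Only a descriptive exposure table and its listing are touched; no primary, efficacy or safety endpoint depends on them. Priority: minor.

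**What to change.** In SAP 7.4.1:

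1. Insert the start dose date in the mono-phase formula.
2. Define the mono phase by the first nivolumab-alone dose, and use the same definition in the duration bullets in place of the fourth-dose gloss.
3. Replace the fixed terms with a denominator valid at every last-dose date, and say which benchmark it represents. Either of these will do:
   - assigned schedule: 1 mg/kg × min(L + 14, 84)/21 + 3 mg/kg × max(L + 14 - 84, 0)/14;
   - subject's own phases: 1 mg/kg × M/21 + 3 mg/kg × (L - M + 14)/14.

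Both equal the present formula, with start date, when four combination doses are given on schedule. They answer different questions: the first shows departure from the arm's plan, the second adherence within the phases actually followed.

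Protocol 4.3.5 and SAP 6.1.2 and 7.4.1 should also be reconciled on the nivolumab dose and schedule after an early switch, so that the planned-dose term matches. That choice is the sponsor's.

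The cost is a few lines of SAP wording and programming. The formulas use only dosing dates, which are already collected.

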3 INVESTIGATIONAL PLAN

3.1 Study Design and Duration

Study Design: This is an exploratory, open-label, multicenter study of nivolumab and nivolumab in combination with ipilimumab.

Approximately 150 subjects with advanced melanoma (unresectable or metastatic) will be treated in this study in four (4) parts. Part 1 of this study will have two (2) cohorts consisting of approximately 40 patients each: cohort 1 will consist of anti-CTLA4 therapy-naïve patients and cohort 2 will consist of patients who have progressed on an anti-CTLA-4 regimen. Cohorts 1 and 2 will be administered nivolumab at 3 mg/kg dose level every 2 weeks. Subjects will go through a **screening period** of no longer than 28 days and eligible subjects will start the **treatment period** for a duration of 2 years depending on their response. Nivolumab will be administered by IV infusion every 14 days in 56 day cycles (on days 1, 15, 29 and 43 of each cycle). Response assessments will be performed on days 49-56. The response assessment must be completed before the first dose in the next cycle.

In Part 2, approximately 20 anti-CTLA4 therapy-naïve patients will be administered nivolumab at 1 mg/kg and ipilimumab at 3 mg/kg every 3 weeks for 4 doses, followed by nivolumab 3 mg/kg alone every 2 weeks (Arm A). This part of the study is aimed at defining the optimal window for on-treatment biopsy with concurrent nivolumab and ipilimumab therapy. All subjects will be required to undergo a pre-treatment biopsy and consent to on-treatment biopsy. Two (2) groups of approximately 10 patients each will be enrolled sequentially with the first group assigned to an on-treatment biopsy between Days 8 and 15 (weeks 2 and 3) after the start of therapy and the second group assigned to an on-treatment biopsy between Days 22 and 29 (subsequent to the second dose of therapy between weeks 4 and 5) after the start of therapy. Optimal biopsy timing will be defined as the biopsy window with the greatest pharmacodynamic

increase in intratumoral activated T cells compared to the pre-treatment biopsy. The defined optimal on-treatment biopsy window will be used in the third part of this study.

In Part 3, approximately 30 anti-CTLA4 therapy-naive patients will be randomized 2:1 and treated with one of the following:

- Arm A: nivolumab 1 mg/kg IV combined with ipilimumab 3 mg/kg IV Q3W for 4 doses then nivolumab 3 mg/kg IV Q2W
- Arm B: nivolumab 3 mg/kg IV Q2W

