6.1.2 Treatment Period

Nivolumab will be given every 2 weeks when administered as monotherapy (Cohorts 1 and 2; Arms B and E; Arms A, C, and D after stopping ipilimumab) and every 3 weeks when administered in combination therapy with ipilimumab. Ipilimumab will be given every 3 weeks when administered as monotherapy (Arm C) or combination therapy (Arms A and D).

On days where both study drugs are given, nivolumab will be given first followed by ipilimumab and will start no sooner than 30 minutes after completion of the nivolumab infusion and after the post-nivolumab pharmacokinetic blood sample is drawn.

The treatment period is defined as starting from the date and time of the first dose of study medication. The treatment period ends 14 days after the last dose of nivolumab, if the last dose is nivolumab, and 21 days after the last dose of ipilimumab, if the last dose is ipilimumab.

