7 STATISTICAL ANALYSES

7.1 General Methods

All analysis will be performed in SAS (Statistical Analysis System software, SAS Institute, North Carolina, USA) using version 9.2 or higher. Some figures may be generated using S-Plus.

Continuous variables will be summarized using descriptive statistics, ie, medians, minimums, maximums and means with standard deviations/standard errors of the mean. Some continuous variables may also be summarized using the geometric mean and coefficient of variation. Categorical variables will be summarized by frequencies and percentages. Percentages will be rounded and, therefore, may not always add up to 100. Percentages less than 0.1 will be indicated as “< 0.1”.

Statistical analyses will be presented by part, cohort, or arm as defined in [Figure 6.1-1](#) and [Table 6.2-1](#). Based on the comparability of data in each part, cohort, or arm, any of the groups may be combined to increase the number of subjects for analyses. The grouping schemes for analyses are further described in the DPP.

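### SAP 7.4.1: the mono-phase nivolumab dose-intensity formula for Arms A and D omits the start date and assumes four combination doses, so early switchers with a last dose before about Day 71 get invalid values

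*SAP*

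**What the plan says.** SAP 7.4.1 gives three nivolumab relative dose intensity formulas. Two of them, for monotherapy arms and for combination subjects who stop in the combination phase, measure time from the start dose date; the second divides by "1 mg/kg*(last dose date - start dose date + 21)/21]*100". The third, for Arm A and D subjects whose last dose is in the mono phase, is "cumulative dose (mg/kg) / [1 mg/kg*4 cycles + 3 mg/kg*(last dose date - 84 + 14)/14]*100". It has no start dose date, and it carries no condition on how many combination doses the subject had.

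The phases are described only in the duration-of-therapy rules of the same section: "if the last dose is nivolumab monotherapy (ie, after the 4th dose in Arms A and D" and "if the last dose is a combination therapy (ie, the first 4 doses in Arms A and D".

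Protocol 4.3.5 says that subjects who must stop for an adverse event while on both drugs "may be allowed to continue therapy with nivolumab only if deemed in their best interest by both the PI and the BMS medical monitor". It does not state the nivolumab dose after such a switch. Protocol 3.1 describes the planned course as four combination doses "followed by nivolumab 3 mg/kg alone every 2 weeks (Arm A". For the interval, SAP 6.1.2 gives nivolumab every 2 weeks as monotherapy, including "Arms A, C, and D after stopping ipilimumab) and every 3 weeks when administered in combination therapy with ipilimumab".

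SAP 7.4.1 reports the ratio by descriptive statistics, in five categories from < 50% to ≥ 110%, and by subject in a listing. SAP 7.1 specifies "medians, minimums, maximums and means with standard deviations/standard errors of the mean".

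**The concern.** The constants 4 and 84 describe one course only: four combination doses and a first nivolumab-only dose 84 days after the first dose. The protocol permits another course, and the subjects who take it have stopped the combination for toxicity. Their exposure differs most from plan, so it is the exposure a reader of the table wants described correctly. If the formula fails for them, a subject who missed no dose can be reported below 50% or above 110%. In an arm of about 10 subjects, one such value can also dominate the mean, standard deviation and range. The missing start date affects every mono-phase subject in these arms, because the text cannot be programmed as printed.

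**Working it through.** **Inputs.** Combination doses of 1 mg/kg nivolumab every 21 days, then 3 mg/kg every 14 days (Protocol 3.1; SAP 6.1.2). Early switch allowed (Protocol 4.3.5). Re-treatment normally within 6 weeks of the previous dose (Protocol 4.3.6). Assumption: 3 mg/kg after an early switch; 1 mg/kg is shown as a check.

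**Notation.** L = days from first to last dose (Day = L + 1); k = combination doses received; n = nivolumab-only doses. Dose received = k + 3n mg/kg.

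**1. Planned course.** With the date read as L, the printed denominator is D = 4 + 3(L - 70)/14. Four combination doses and one nivolumab-only dose at L = 84 give 7/7 = 100%, so this is the intended reading. Study day (85) in place of L gives 7/7.214 = 97%. A raw calendar date does not work: stored as, say, 20,000 days, it gives 7/4274.7 = 0.16%.

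**2. Zero of the denominator.** D = 0 at L = 70 - 56/3 = 51.3, so D is negative for a last dose up to about Day 52.

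**3. On-schedule early switch.** The first nivolumab-only dose is 21 days after the last combination dose, so L = 21k + 14(n - 1). No dose is missed.

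| k | n | Day of last dose | Received | Printed D | Intensity |
|---|---|---|---|---|---|
| 1 | 1 | 22 | 4 | -6.5 | -62% |
| 1 | 2 | 36 | 7 | -3.5 | -200% |
| 1 | 3 | 50 | 10 | -0.5 | -2000% |
| 1 | 4 | 64 | 13 | 2.5 | 520% |
| 2 | 1 | 43 | 5 | -2.0 | -250% |
| 2 | 2 | 57 | 8 | 1.0 | 800% |
| 3 | 1 | 64 | 6 | 2.5 | 240% |

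At 1 mg/kg after the switch, the first nivolumab-only dose still gives 2/-6.5 = -31%, 3/-2 = -150% and 4/2.5 = 160% for k = 1, 2, 3.

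**4. Switch after a 6-week gap.** k = 1: 4/-2 = -200% (Day 43), then 7/1 = 700% (Day 57). k = 2: 5/2.5 = 200% (Day 64). k = 3: 6/7 = 86% (Day 85), a plausible value.

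**5. Phase set by dose count.** If a subject stays in the combination phase through the fourth dose of any kind, the divisor is (L + 21)/21. On schedule, k = 1 gives 4/2 = 200%, 7/2.667 = 262.5% and 10/3.333 = 300%. k = 2 gives 5/3 = 167% and 8/3.667 = 218%. k = 3 gives 6/4 = 150%. From the fifth dose the mono formula applies: 13/2.5 = 520% for k = 1 at Day 64.

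**6. From L = 70.** Planned dose through L + 14 is 4 + 3(L + 14 - 84)/14 = 4 + 3(L - 70)/14, which is the printed D. Before that, planned dose prorated at 1 mg/kg per 21 days is (L + 14)/21. At L = 63 this is 3.67 against the printed 2.5, so even measured against the arm's plan the k = 3 subject should show 6/3.67 = 164%, not 240%.

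Later on-schedule values for k = 1, 2, 3 are 37/26.5 = 140%, 35/28 = 125% and 30/26.5 = 113% at about 6 months. At about 1 year they are 76/65.5 = 116%, 74/67 = 110% and 69/65.5 = 105%. At 1 mg/kg after the switch, k = 1 at Day 176 gives 13/26.5 = 49%.

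**7. Effect on a summary.** One -2000% with nine Arm D subjects at 100%: mean (900 - 2000)/10 = -110%, SD 664, median 100%. One 240%: mean (900 + 240)/10 = 114%, median 100%.

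**The case against.** The strongest reply is that SAP 7.4.1 measures intensity against the arm's planned regimen, and step 6 supports this from L = 70. A subject who moves early to 3 mg/kg every 2 weeks has received 37 mg/kg by Day 176 against 26.5 planned, and 140% reports that truthfully. This stands. A reader might infer that every high value in an early switcher is wrong, including plausible ones near 105% to 140% a year into treatment. The documents do not support that, because they do not say that the reference regimen changes at the switch.

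Second, the phase wording may set the phase by dose count, and then the negatives largely disappear. This also stands: an on-schedule subject's fifth dose cannot come before L = 63, where D is 2.5. But that reading divides 3 mg/kg doses by a 1 mg/kg every-3-weeks plan (150% to 300%), so it replaces one fault with another. The wording also sits in the duration rules, not in the dose-intensity rules.

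Third, the worst cases are uncommon. The switch is case by case and follows an adverse event that must normally resolve first, and -2000% needs exactly three on-time nivolumab doses and then a stop. That is fair, and longer gaps shrink the error. A 6-week gap still gives -200%, then 700%, after one combination dose.

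Fourth, the missing start date is an evident slip whose intent the other formulas show. Agreed, but it needs correcting because the expression cannot be programmed as printed.

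**Conclusion.** The point holds within limits. The printed formula is not a duration as written. Under its evident meaning it is invalid for early switchers with a last dose before about Day 71: negative up to about Day 52, then grossly inflated. Values after that are a question of definition, not a demonstrated error, and at 1 mg/kg after the switch they would not be high.

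The sizes rest on two assumptions: elapsed days since first dose, and 3 mg/kg every 2 weeks after the switch. The negative values also require that a nivolumab-only dose counts as mono phase whatever its number.

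The documents give no early-switch rate. If 10% to 30% of about 50 Arm A and D subjects switched early, that would be 5 to 15, of whom only those stopping before about Day 71 get a clearly wrong value.

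A reader might also infer that tolerability or activity conclusions are at risk. They are not: biomarker, efficacy and adverse-event results do not use this ratio, the number of doses and cumulative dose are reported separately, and the median barely moves. The effect is confined to the descriptive exposure table and listing.

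**What to change.** In SAP 7.4.1:

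1. Define the mono phase by the first nivolumab-only dose, not by the fourth dose. Do the same in the duration rules, where the phase decides whether 14 or 21 days are added, a difference of one week.
2. With k = combination doses received, use denominator = 1 mg/kg*k + 3 mg/kg*(last dose date - start dose date - 21k + 14)/14.
3. State that intensity is relative to the regimen the subject is following.

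At k = 4 this is the intended formula, so four-dose subjects do not change. It exceeds the printed denominator by 3.5(4 - k), that is 10.5, 7.0 and 3.5 mg/kg for k = 1, 2, 3. It gives (k + 3n)/(k + 3n) = 100% for every on-schedule early switch. If the dose after an early switch is not 3 mg/kg, that dose should replace the 3.

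The small downside is that a delay before the switch is charged at the monotherapy rate. With a 6-week gap, the first nivolumab-only dose gives 4/8.5 = 47%, 5/9.5 = 53% and 6/10.5 = 57% for k = 1, 2, 3. The printed formula already does this to a four-dose subject (7/11.5 = 61%).

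An alternative charges the gap at the combination rate: 1 mg/kg*(first nivolumab-only date - start date)/21 + 3 mg/kg*(last dose date - first nivolumab-only date + 14)/14. It gives 80%, 83% and 86%, but moves the delayed four-dose subject from 61% to 7/8 = 87.5%, so the sponsor would have to accept that change.

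The cost is one formula and one phase definition. Dose dates and amounts are already collected, and no protocol change is needed.
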